PROTOCOL TITLE:

HIS BUNDLE PACING VERSUS CORONARY SINUS PACING FOR CARDIAC RESYNCHRONIZATION THERAPY

PI: [name] AND [name]

CO-I(S): [name]; [name] PHD; [name]; [name]; [name]

FUNDING: INTERNAL

SPONSOR: NONE

TYPE OF RESEARCH: CLINICAL TRIAL

INTERVENTION: IMPLANTATION OF CARDIAC RESYNCHRONIZATION THERAPY DEVICE

MANUFACTURER OF INTERVENTION: NOT APPLICABLE

IND OR IDE # NOT APPLICABLE

Contents

1. Introduction.....	6
A. Background and Rationale	6
B. Objectives.....	7
2. Study Design.....	7
3. Subject Selection and Withdrawal.....	8
4. Study Device.....	10
5. Study Procedures	10
6. Statistical Plan and Considerations.....	12
7. Risks and Benefits.....	12
8. Safety and Adverse Events	13
9. Data handling and Record Keeping	13
10. Study Monitoring, Auditing and Inspecting	13
11. Financial Considerations.....	13
12. Ethical Considerations	13
13. Conflict of Interest	13
14. References.....	14
A. Questionnaire	16
B. Schedule of Events (schema)	17

STUDY SUMMARY

TITLE	His-bundle pacing versus coronary sinus pacing for cardiac resynchronization therapy (CRT)
SHORT TITLE	The His-Sync Study
PROTOCOL NUMBER	UofC & Baptist Health Louisville: IRB15-1728 UCLA: IRB#15-000464 NWU: STU00202920 Geisinger: 2017-0339 IU: 1707220499 Rush: 16100902-IRB01 Edward: HIS-SYNCH
METHODOLOGY	Single-blind clinical trial
STUDY DURATION	12 months
STUDY CENTER(S)	Multi-center; also enrolling patients at the University of California Los Angeles (UCLA) Medical Center, Northwestern University (NWU), Geisinger Wyoming Valley Medical Center (Geisinger), Indiana University (IU), Rush University Medical Center (Rush), Edward Hospital (Edward), and Baptist Health Louisville
OBJECTIVES	To compare the effectiveness of his-bundle pacing versus coronary sinus LV lead localization in patients with heart failure.
NUMBER OF SUBJECTS	40 patients total
DIAGNOSIS AND MAIN INCLUSION CRITERIA	
Patients with heart failure (HF) eligible for CRT as part of routine standard-of-care based on accepted Class I or Class II indications will be considered for this study. Inclusion criteria include:
 
 1) Left ventricular ejection fraction (LVEF) $\leq 35\%$, sinus rhythm (SR), left bundle-branch block (LBBB) morphology, and QRS duration ≥ 150 msec, and NYHA Class II, III, or ambulatory Class IV patients on goal-directed medical therapy (GDMT) [Class I] 2) LVEF $\leq 35\%$, SR with LBBB with QRS 120-149 msec on GDMT [Class IIa] 3) LVEF $\leq 35\%$, SR with non-LBBB with QRS ≥ 150 msec on GDMT [Class IIa] 4) LVEF $\leq 35\%$, in AF if medication or AV nodal ablation will allow near 100% pacing [Class IIa] 5) LVEF $\leq 35\%$ undergoing new or replacement device with anticipated $>40\%$ ventricular pacing on GDMT

	
[Class IIa]
 
6) LVEF $\leq 30\%$, ischemic etiology of HF, SR with LBBB ≥ 150 msec and NYHA Class I symptoms on GDMT [Class IIb]
 
7) LVEF $\leq 35\%$, SR with non-LBBB with QRS 120-149 msec, NYHA Class III/ambulatory Class IV HF on GDMT [Class IIb]
 
8) LVEF $\leq 35\%$, SR with non-LBBB with QRS ≥ 150 msec, NYHA Class II HF on GDMT [Class IIb]

STUDY PRODUCT	
His-Bundle lead placement will require use of Medtronic delivery sheath (C315 HIS, Medtronic, Minneapolis, MN) and pacemaker lead (Select Secure 3830, Medtronic, Minneapolis, MN) for patients randomized to His bundle pacing. These are FDA approved for routine clinical use.
 
Coronary sinus LV leads utilized in the study will be FDA approved leads per the discretion of the implanting physician

DURATION OF ADMINISTRATION	Pacing will be delivered throughout the duration of the study, with goal pacing delivery of 95%, as is the standard-of-care for patients receiving CRT
REFERENCE THERAPY	The reference therapy will be the control group; i.e., those patients assigned to CRT with use of a CRT
STATISTICAL METHODOLOGY	Traditional statistical methods will be employed. The student's T-test will be used for continuous comparisons. Fisher's exact or the Chi-square test will be applied for dichotomous variables. Time to endpoint analysis will be performed using the Kaplan-Meier method.

LIST OF ABBREVIATIONS

ACE-I	ANGIOTENSIN-CONVERTING ENZYME INHIBITOR
AF	ATRIAL FIBRILLATION
ARB	ANGIOTENSIN RECEPTOR BLOCKER
BB	BETA-BLOCKER
CRT	CARDIAC RESYNCHRONIZATION THERAPY
CS	CORONARY SINUS
FDA	FOOD AND DRUG ADMINISTRATION
GDMT	GOAL-DIRECTED MEDICAL THERAPY
HBP	HIS BUNDLE PACING
HF	HEART FAILURE
ICD	IMPLANTABLE CARDIOVERTER-DEFIBRILLATOR
IRB	INSTITUTIONAL REVIEW BOARD
LBBB	LEFT BUNDLE-BRANCH BLOCK
LV	LEFT VENTRICULAR
LVEF	LEFT VENTRICULAR EJECTION FRACTION
NYHA	NEW YORK HEART ASSOCIATION
RA	RIGHT ATRIUM
RBBB	RIGHT BUNDLE-BRANCH BLOCK
RV	RIGHT VENTRICLE
SR	SINUS RHYTHM
TTE	TRANSTHORACIC ECHOCARDIOGRAM
UCMC	UNIVERSITY OF CHICAGO MEDICAL CENTER
UOFC	UNIVERSITY OF CHICAGO
VF	VENTRICULAR FIBRILLATION
VT	VENTRICULAR TACHYCARDIA

1. INTRODUCTION

A. BACKGROUND AND RATIONALE

Heart failure has been characterized as the singular epidemic of contemporary cardiovascular medicine. At 40 years of age, the lifetime risk of developing heart failure is one in five.¹ The prevalence of heart failure exceeds 5.3 million in the United States, and accrued estimated direct and indirect costs totaling \$39.2 billion in 2010.^{1,2} During the past two decades, cardiac resynchronization therapy (CRT) has emerged as a safe and efficacious device-based therapy for heart failure patients with severe systolic dysfunction and intraventricular conduction delay.³⁻⁵ CRT is the use of a pacemaker with three electrical leads to coordinate myocardial contraction. Two leads are endocardial, placed in the right atrium (RA) and right ventricle (RV), while a third lead is traditionally placed in a tributary of the coronary sinus overlying the epicardial surface of the left ventricle (LV). CRT exerts its physiological impact via synchronizing ventricular contraction, leading to improved left ventricular filling, and pumping efficiency. Multiple prospective randomized studies have shown that CRT yields long-term clinical benefits, including improved quality of life, increased exercise capacity, reduced heart failure hospitalization and decreased all-cause mortality.⁶⁻¹¹

Despite dramatic impact and expanding indications, however, there remain significant barriers to realizing the overall potential benefit of CRT. Most notably, up to one-third of patients treated with CRT do not derive *any* detectable clinical or echocardiographic benefit, and indeed, some worsen after resynchronization.^{3,12} Intrinsic patient and myocardial substrate characteristics *a priori* may limit response in some patients. Additionally, intraprocedural factors—particularly the location of the left ventricular (LV) lead—may also effect longer term outcome. In particular, recent analysis from MADIT-CRT and other studies showed that an LV lead placed in an anatomically apical region of the heart is associated with a worse clinical outcome.^{13,14} Distinct and complementary to anatomical localization, characterization of the LV lead with respect to the heart's electrical activation pattern has been shown to be an important determinant of response.¹⁵⁻¹⁸ Effective integration of anatomical and electrical data in order to guide LV lead placement for CRT is still actively being explored.

More recently, the feasibility of resynchronizing ventricular activation by permanent pacing of the His bundle region has been described, with clear clinical advantages over traditional RV apical pacing.¹⁹⁻²³ This technique is an FDA approved therapy for pacing. The physiologic benefit of permanent His bundle pacing (HBP) is the ability to stimulate the ventricles through the intrinsic His-purkinje system, which results in synchronous electrical and mechanical activation. Furthermore, similar to CRT, reports of hyper-response—typically described as patient functional recovery to an LVEF $\geq 50\%$, has been reported with HBP after restoration of normal intrinsic conduction.²⁴⁻²⁶ Perhaps even more provocatively, in a recent study in which patients were implanted with four leads (RA, RV, CS LV lead, and HBP lead), both modes of resynchronization (HBP and CS) were studied utilizing a cross-over design, and both were found to be associated with similar benefit (with patients acting as their own controls).²⁷ Indeed, HBP may have theoretical advantages over CRT using a coronary sinus lead, which is associated with limited coronary venous anatomy and complications that include coronary sinus dissection, venous perforation, and the potential for proarrhythmia. While both techniques comprise the standard-of-care for pacing, direct comparison of HBP with traditional

CS lead position for CRT has not yet been investigated, and is the motivation behind the His-SYNC Study.

B. OBJECTIVES

We hypothesize that:

- a. In patients with advanced heart failure and evidence of intraventricular conduction delay who meet criteria for CRT, HBP may be safely achieved *and*
- b. HBP is associated with similar echocardiographic and clinical outcome as conventional CS pacing during CRT

Specific aims:

Aim 1: To determine the overall rate of successful His-bundle lead placement at the time of implant of CRT. Patients randomized to HBP but who cannot be successfully implanted with a HBP lead will cross-over to traditional CS lead position.

Aim 2: To assess the impact of HBP versus CS pacing on acute and mid-term outcomes.

Acute outcomes include incidence of periprocedural complication and change in QRS duration pre-and post-pacing. Mid-term outcomes include echocardiographic response at 6 and 12 months along with a composite clinical outcome of heart failure hospitalization, arrhythmia, and all-cause mortality.

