- **Clinical:** Primary clinical endpoint is a composite of heart failure hospitalization, VT/VF, and any-cause mortality at 12 months.
- **Electrocardiographic:** Change in QRS duration between pre-implant and at hospital discharge, 3 months, 6 months, and 12 months will be performed by readers blinded to treatment allocation. Arrhythmia occurrence (i.e., AF, nonsustained VT, VT or VF requiring device therapy) will be documented throughout the study period
- **Echocardiographic:** Change in left ventricular ejection fraction, chamber dimension, and tissue-strain pre-implant, at 6 months, and at 12 months to be performed by readers blinded to treatment allocation

Primary safety endpoint: Procedure-related complications will be assessed prospectively both acutely and throughout the study period, including:

- **Procedure related:** pneumothorax, perforation, pericardial effusion, or hemorrhage
- **System related:** implant site hematoma, implant site infection
- **Lead related:** lead dislodgement, lead fracture, inability to pace due to high threshold, phrenic capture

Randomization scheme: Patients will be allocated to HBP or standard CS lead at time of implant. Patients with LBBB and non-LBBB will be assigned to separate blocks and randomized separately.

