6. STATISTICAL PLAN AND CONSIDERATIONS

Sample size estimation:

The sample size for this study is a total of 40 subjects (20 HBP and 20 CS lead). The sample size estimate was based on a goal to observe an absolute 10% difference in LVEF between the two groups, leading to a Cohen's d statistic of 1. With a significance level (α) = 0.05 and a power of 0.8, at least 17 subjects will be required in each group. A goal of 40 subjects was made to allow for possible dropout during the study period.

Statistical methods:

Patients will be studied based on the final treatment allocation. Crossovers and reasons for crossover will also be recorded. Fisher's exact or the Chi-Square test will be used for categorical variables, and continuous parameters will be compared by the two-tailed unpaired Student's t test and the F test for analysis of variance (ANOVA), as needed. Kaplan-Meier method will be used for computing the event free survival curves. Each implant strategy will be compared within this cohort of patients for its impact on percent change QRS duration, LVEF, and as clinical outcome. Multiple logistic regression and multiple regressions using the Cox proportional hazards model will be performed to determine the independent association of each of the implant variables with LVEF and clinical outcome.

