10. STUDY MONITORING, AUDITING AND INSPECTING

All periprocedural complications and adverse events will be reviewed by PIs at study midpoint to ensure there is no significant difference in event rate between the study groups. Should there be significant differences, or if there should be a high overall event-rate out-of-line with the procedural norm for CRT, the study will be halted.

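### The plan hypothesises that His-bundle pacing is safe but sets no criterion or interval for it, and a non-significant comparison of 20 v 20 patients would be weak evidence of safety

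*Combined protocol and SAP*

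**What the plan says.** Hypothesis (a) in Section 1.B is a positive claim about patients who meet criteria for resynchronization: "HBP may be safely achieved". It carries no threshold and no comparator. Aim 2 in the same section then makes complications an HBP-versus-CS outcome: "Acute outcomes include incidence of periprocedural complication and change in QRS duration pre-and post-pacing".

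Section 2 sets complications as the primary safety endpoint, in procedure-, system- and lead-related groups: "Procedure-related complications will be assessed prospectively both acutely and throughout the study period".

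Section 6 does not mention safety. The sentence that would cover a yes/no complication outcome is general: "Fisher's exact or the Chi-Square test will be used for categorical variables". The trial size of 20 per arm is justified by ejection fraction alone, from a "goal to observe an absolute 10% difference in LVEF between the two groups". Section 6 also analyses patients by the treatment they finally received.

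Section 10 has the investigators review events at the midpoint "to ensure there is no significant difference in event rate between the study groups". It would halt the study for significant differences or for an overall rate above an unquantified procedural norm. Section 8 places the review at 20 combined patients and would halt for a trend, also unquantified.

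**The concern.** A claim of safety needs evidence that rules out an unacceptable complication rate. A test of difference can show harm, but failing to show harm does not establish safety, least of all in a trial sized for another outcome. The plan offers nothing else: no acceptable limit, no margin and no interval. Section 10 shows the document itself drawing comfort from non-significance, at least for continuing the study.

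The final report could therefore present a non-significant complication comparison as support for hypothesis (a), while the data remained compatible with a rate under HBP several times that under CS pacing. Nothing in the plan guards against that.

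**Working it through.** **The plan's own figure.** Section 6 states: "With a significance level (α) = 0.05 and a power of 0.8, at least 17 subjects will be required in each group". For a two-sided t test with Cohen's d = 1, the noncentral t gives power 0.781 at 16 per group, 0.807 at 17 and 0.869 at 20. The figure of 17 reproduces, but it concerns ejection fraction and says nothing about complications.

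**Inputs for safety.** 20 v 20 patients (Section 6); one indicator per patient for at least one listed complication; two-sided 0.05. Section 6 states two tails only for the t test, so sidedness here is an assumption. No CS complication rate is given, so rates are assumed and varied.

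**Step 1: results that need no assumed rate.** The two-sided Fisher p-value with equal arms is twice the hypergeometric tail (HBP v CS):
- 4 v 0: 2 × C(20,4)/C(40,4) = 2 × 4,845/91,390 = 0.106
- 6 v 1: 2 × [C(20,6)·C(20,1) + C(20,7)]/C(40,7) = 2 × 852,720/18,643,560 = 0.091
- 8 v 2: 2 × [C(20,8)·C(20,2) + C(20,9)·C(20,1) + C(20,10)]/C(40,10) = 2 × 27,478,256/847,660,528 = 0.065

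The last is an observed fourfold excess, 40% v 10%. Fisher reaches 0.05 only from 5 v 0, 7 v 1 or 9 v 2.

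Uncorrected chi-square, N(ad − bc)²/(product of the margins), gives for the same tables:
- 4 v 0: 40 × 80²/(4 × 36 × 20 × 20) = 4.44, p = 0.035
- 6 v 1: 40 × 100²/(7 × 33 × 20 × 20) = 4.33, p = 0.037
- 8 v 2: 40 × 120²/(10 × 30 × 20 × 20) = 4.80, p = 0.028

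So all three tables change sides depending on which of the two permitted tests is used.

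**Step 2: power to show HBP worse.** Power = Σ over tables (x, y) with x > y and p ≤ 0.05 of Bin(x; 20, p_HBP) × Bin(y; 20, p_CS). The last column repeats this for 10 v 10, the approximate split at the midpoint.

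| Assumed CS rate | HBP rate | Fisher, 20 v 20 | Chi-square, 20 v 20 | Fisher, 10 v 10 |
|---|---|---|---|---|
| 5% | 15% (×3) | 7.0% | 15.3% | 0.6% |
| 5% | 20% (×4) | 16.8% | 29.2% | 2.0% |
| 10% | 30% (×3) | 24.2% | 35.7% | 5.7% |
| 10% | 40% (×4) | 49.2% | 62.3% | 15.2% |
| 15% | 45% (×3) | 44.3% | 57.2% | 14.1% |
| 15% | 60% (×4) | 79.7% | 87.3% | 34.9% |

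Fisher's power passes 50% at a CS rate of about 16.5% for a tripling and 10.5% for a quadrupling.

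**Step 3: what an interval would say.** Exact (Clopper-Pearson) two-sided 95% limits for 20 HBP patients:
- 0 events: upper limit 1 − 0.025^(1/20) = 16.8%
- 1 event: 0.1% to 24.9%
- 2 events: 1.2% to 31.7%

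**The case against.** The strongest reply is that no passage says hypothesis (a) will be decided by a significance test. Section 6 is generic, allows two tests and names neither safety nor the hypothesis. A reader might infer that the plan declares HBP safe if Fisher's test is non-significant. The documents do not say so; the gap is that they provide no other criterion.

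A reader might also infer that no estimate is planned. That goes too far: Aim 1 calls for a success rate and Aim 2 for a complication incidence, so point estimates are intended and only intervals are missing.

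Nor does safety oversight rest on significance alone. Sections 8 and 10 also halt for a trend or a high overall rate, neither of which requires a significant difference. Both are unquantified, and both govern continuation at the midpoint rather than the final conclusion. The two sections also state the halting condition differently and must be reconciled.

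Finally, it is tempting to say that the trial would miss a tripling or quadrupling most of the time. That depends on a CS rate the documents do not give. The endpoint is broad, including hematoma, dislodgement, high threshold and phrenic capture, so rates above 10% cannot be excluded, and detection is then much better. Chi-square also finds more. These points limit the size of the concern but do not supply a criterion or an interval.

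**Conclusion.** The concern holds in a limited form. The plan states a safety hypothesis and a primary safety endpoint without saying what would count as safe, and the only comparison it offers cannot establish safety at this size. At assumed CS rates of 5-10%, Fisher's power at 20 v 20 is 7-24% for a tripling and 17-49% for a quadrupling; at 15% it is 44% and 80%. The Fisher results for 4 v 0, 6 v 1 and 8 v 2 need no assumed rate, but they do not carry over to uncorrected chi-square.

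The calculations assume a two-sided 0.05 test, one indicator per patient and equal arms. Crossover with analysis by final treatment could make the arms unequal. It could also count a complication of a failed HBP attempt under CS, which would make HBP look safer than it was. The documents do not support a claim that large increases would be missed whatever the CS rate.

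**What to change.** In Section 6, make estimation the analysis of the primary safety endpoint:

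- Report the proportion of patients with at least one listed complication by randomized arm, and also by final treatment, each with an exact (Clopper-Pearson) 95% interval.
- Report the HBP-minus-CS risk difference with a 95% score interval.
- State that a non-significant test will not be read as evidence of safety.
- Word the conclusion on hypothesis (a), and Section 1.B to match, in terms of the complication rates that the interval excludes.
- Report the Aim 1 implant success rate with an exact 95% interval.

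This takes a few sentences in Sections 1.B and 6. It needs no extra patients, no new data beyond what is already collected and no choice of margin. The price is a more modest claim: even with no complications in 20 HBP patients, the report could say only that rates above 16.8% are excluded.

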2. STUDY DESIGN

Study design: Single-blind study. Patients will be randomized, at the time of implant, to HBP versus CS pacing, and remain blinded to their treatment allocation. Both treatment options use standard-of-care, FDA-approved devices. The distinction is only in the allocation toward HBP and CS pacing. Treating physicians will be aware of assignment in order to facilitate routine device follow-up. Echocardiographic and electrocardiographic evaluation will also be performed in a blinded manner.

Cross-over is permitted between treatment group allocation if:

- CS lead cannot be placed due to difficult cannulation of the CS, limited branches at the posterolateral or lateral wall, or phrenic nerve capture. These patients may then cross-over to HBP.
- HBP patients may cross-over if lead cannot be positioned with adequate stability and reasonable pacing output or if QRS width does not narrow by at least 20% or to a QRS width of \leq 130 msec.

Implant procedure will be per routine percutaneous access, as is standard for pacemaker and ICDs. All patients will receive an FDA-approved cardiac resynchronization therapy pacemaker or defibrillator device, as per standard of care outlined for the patient. In order to facilitate optimal lead placement, arterial access for levo-phase CS angiography and/or LV septal mapping to characterize site of bundle-branch block may also be performed, at the discretion of the implanting physician per his/her standard practice.

Follow-up will be performed at 2 weeks post-implant for incision check and device interrogation as is standard of care. In addition, routine device and clinical follow-up will be scheduled at 1, 3, 6, and 12 months.

Electrocardiography (i.e., ECG) will be performed pre-implant, prior to hospital discharge, at 3 months, 6 months, and 12 months. Echocardiography will be performed pre-implant, 6 months, and 12 months to evaluate for change in LVEF, chamber dimension, and wall motion with strain imaging as is standard of care in the treatment of patients with advanced heart failure. NYHA functional class and quality of life (utilizing the Kansas City Cardiomyopathy Questionnaire) will be assessed pre-implant and at 6 months.

Duration of study: 12 months

Primary endpoints: A combination of clinical, electrocardiographic, and echocardiographic endpoints will be prospectively studied. These include:

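### Hypothesis (b) says HBP and CS pacing give similar outcomes, but the plan tests only for a difference and has no rule for concluding similarity, so it can count against (b) but cannot confirm it.

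*Combined protocol and SAP*

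**What the plan says.** Section 1.B (Objectives) gives two hypotheses. Hypothesis (a) is that HBP can be achieved safely in patients who meet CRT criteria. Hypothesis (b), the only one about comparative outcome, is that "HBP is associated with similar echocardiographic and clinical outcome as conventional CS pacing during CRT".

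The rest of the plan describes a comparison for difference:

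- **Study Summary, Objectives:** "To compare the effectiveness of his-bundle pacing versus coronary sinus LV lead localization", which is neutral as to direction.
- **Section 6, Sample size estimation:** the size was "based on a goal to observe an absolute 10% difference in LVEF between the two groups", with Cohen's d of 1, alpha 0.05, power 0.8 and at least 17 per group. This is raised to 20 per group (40 in all) for dropout.
- **Section 6, Statistical methods:** "continuous parameters will be compared by the two-tailed unpaired" Student's t test and ANOVA as needed. Fisher's exact or chi-square tests serve categorical variables, Kaplan-Meier serves event-free survival, and logistic and Cox models serve association. The Study Summary lists the same kinds of test ("T-test will be used for continuous comparisons") but contains no sizing.
- **Section 2, Primary endpoints:** "Primary clinical endpoint is a composite of heart failure hospitalization, VT/VF, and any-cause mortality at 12 months". No event rate or power is given for it.

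There is no equivalence or non-inferiority margin, no confidence-interval criterion and no other statement of what result would count as similar.

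**The concern.** A test of difference takes no difference as its null hypothesis. It can reject that null, which here would be evidence against (b). Failing to reject it is not evidence for (b), because a small trial often fails to reject when a real difference exists. Confirming similarity needs the reverse: a stated amount of difference that would be too large, and an interval or test able to exclude it.

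The plan supplies neither. If LVEF and the composite both come out non-significant, nothing in the protocol says how that bears on (b). The reading would then be settled after the data are seen, and the wording of (b) invites the conclusion that the two strategies have been shown to be alike. With 40 patients that conclusion could stand beside an LVEF difference of several points, or a large relative difference in clinical events.

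**Working it through.** **Inputs from section 6.** Difference to detect: 10 LVEF points. Cohen's d = 1. Two-sided alpha 0.05, power 0.8. At least 17 per group needed, 20 per group planned.

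**Implied SD.** SD = difference / d = 10 / 1 = 10 points. The SD itself is not stated, and section 6 does not say whether d refers to LVEF at follow-up or to change in LVEF. The endpoint in section 2 is change.

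**Step 1: reproduce the plan's figure.** Two-sided unpaired t test, noncentral t with df = 2n − 2 and noncentrality d × √(n/2).

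- n = 16: noncentrality √8 = 2.83, power 0.781.
- n = 17: noncentrality √8.5 = 2.92, power 0.807.
- n = 20: noncentrality √10 = 3.16, power 0.869.

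The smallest n that reaches 0.8 is 17, as stated. A one-sided calculation gives 13 (normal approximation) and does not match. The stated size is therefore a correct two-sided calculation for detecting a difference.

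**Step 2: what a result can exclude.** Expected 95% CI half-width, taking the sample SD as 10: t(0.975, 2n − 2) × 10 × √(2/n).

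- n = 17: 2.037 × 10 × 0.343 = 7.0 points.
- n = 20: 2.024 × 10 × 0.316 = 6.4 points.

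These are also the observed differences needed for significance. Even if the two groups had identical mean LVEF, the interval would run to about 6 or 7 points in each direction.

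**Step 3: how often a real difference is missed.** Assume a true difference of 5 points (an assumption; the documents give no such figure), so d = 0.5.

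- n = 17: noncentrality 0.5 × 2.92 = 1.46, P(non-significant) = 0.707.
- n = 20: noncentrality 0.5 × 3.16 = 1.58, P(non-significant) = 0.662.

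At a true difference of 10 points, the plan's own target, the figures are 1 − 0.807 = 0.193 and 1 − 0.869 = 0.131.

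**Step 4: the clinical composite.** The documents give no event rate, so the rates here are assumed and purely illustrative. There are 20 per group, with exact enumeration over two binomial distributions, and the true rate in one group is double that in the other. Both categorical tests named in section 6 are shown; the chi-square is uncorrected.

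| Assumed rates | Fisher, P(non-significant) | Chi-square, P(non-significant) |
|---|---|---|
| 10% v 20% | 0.928 | 0.862 |
| 20% v 40% | 0.808 | 0.709 |
| 30% v 60% | 0.653 | 0.537 |

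Across this range, a doubling of events would be non-significant more often than not.

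**The case against.** The best defence is that (b) expresses an expectation rather than a claim to be tested. It echoes the earlier crossover study described in section 1.A, which found comparable benefit from the two modes. The stated objective, Aim 2 and the sample size all describe a small two-sided comparison, and on that reading nothing in the operative plan is inconsistent. Much of this stands, and it limits the point to (b). The objective and Aim 2 are neutral comparisons, while hypothesis (a) and Aim 1 concern HBP alone (safety and implant success), so none of them is affected. But (b) is listed as a formal hypothesis, and neutral wording elsewhere does not supply a rule for judging it.

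Three stronger readings are tempting, and the documents do not support them:

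- *The sample size is wrong.* It is not: 17 per group is right for the test it was computed for. The fault is the missing rule.
- *The trial intends to read p > 0.05 as similarity.* No section says so. The wording of (b) invites that reading and the plan offers no alternative, but it is a risk and not a stated intention.
- *The 10-point figure is a similarity margin.* Section 6 presents it only as the difference to be detected, and nothing in the documents supports it as an acceptable loss of LVEF.

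It is also fair to say that the 5-point difference and the composite event rates are assumptions. The conclusion does not rest on them. It rests on the missing rule, and the half-widths follow from the plan's own inputs.

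**Conclusion.** The concern holds, limited to hypothesis (b). Followed exactly, the plan can produce evidence against (b) but has no valid route to confirming it, for LVEF or for the composite. This is more than a missing detail, because (b) is the only stated hypothesis on comparative outcome. It is worth correcting, but it does not undermine the sample size or the planned difference tests.

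The scale depends on the implied SD of 10 and on equal groups of 17 to 20. If the SD of the LVEF measure actually analysed differs from 10, the half-widths scale in proportion. The composite figures show only that 40 patients are too few for a non-significant result to be reassuring under the assumed rates.

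**What to change.** **1. Reword (b) as estimation.** This resolves the problem on its own. Suggested text: *To estimate the HBP minus CS difference in LVEF change and in the 12-month clinical composite, each with its 95% confidence interval. A p-value above 0.05 will not be interpreted as evidence of similarity.* State in section 6 which LVEF measure the SD refers to.

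**2. Only if a similar or not-worse claim for LVEF is to be kept,** fix the following before data are seen, and state the power of the resulting rule:

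- the margin, with its justification;
- the time point, since both 6 and 12 months are listed;
- the interval that governs the conclusion;
- the analysis population. Section 2 says "Cross-over is permitted between treatment group allocation if" certain implant conditions arise, in either direction, and section 6 says "Patients will be studied based on the final treatment allocation". A similarity rule should say openly whether it applies to that grouping, to the randomised groups or to both.

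**Cost.** Protocol and SAP wording only, with no extra patients. The price is a narrower claim: the trial would report how large a difference remains compatible with the data, and no similarity claim would be available for the clinical composite.
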